*** Radioisotopes or Radiation Machines ***

You selected NO for Radioisotopes in the General Checklist. If you would like to add Radioisotopes, change the selection to YES in general Checklist.

4.

Radioisotopes or Radiation Machines Please note: For projects requiring radiation procedures, please contact the CSU Radiation Control Office (RCO). For more information see:
<http://www.ehs.colostate.edu/WRad/Home.aspx> :

a) If applicable, summarize in lay language the radiographic diagnostic and therapeutic procedures associated with this protocol.

Body composition will be measured by dual energy x-ray absorptiometry (DEXA) at pre and post treatment

b)

Are the radiation procedures being performed a normal part of the clinical management for the medical condition that is under study (Standard of Care) or are the procedures being performed because the research subject is participating in this project (extra CT scans, more fluoroscopy time, additional Nuclear

Protocol Title: Does Dapagliflozin Provide Additional Health Benefits To Dietary Counseling For Weight Loss?
Clinical Research Protocol Title: Dapagliflozin Promotes Favorable Health Benefits That Are Independent Of Weight Loss In Overweight/Obese Adults

Protocol Type: Biomedical

Date Submitted: 03/01/2018

Approval Period: Draft

Important Note: This Print View may not reflect all comments and contingencies for approval. Please check the comments section of the online protocol.
Questions that appear to not have been answered may not have been required for this submission.
Please see the system application for more details.

Medicine Studies, etc.,) (Not Standard of Care)? If some procedures are Standard of Care and some are Not Standard of Care, check both boxes.

NOT STANDARD OF CARE

If it is not standard of care, complete the rest of this section. Provide the CSU RCO approval information

X STANDARD OF CARE

If it is only standard of care, skip the rest of this section.

CSU Radiation Control Office approved protocol number:

CSU Radiation Control Office protocol approval date:

For more information, see the RCO website at: <http://www.ehs.colostate.edu/Wrad/home.aspx> or Contact: [name], Radiation Safety Officer, at [contact].

*** * * Medical Equipment for Human Subjects and Laboratory Animals; Investigational Devices * * *****5. Medical Equipment for Human Subjects**

If medical equipment is being used for human subjects/patients, describe this equipment and indicate if the use is normal practice for the population under study. You may have already described this equipment in the Study Procedures section. If you have already listed this information in the Study Procedures Section, please do not duplicate this information here. In the space below, input N/A if not applicable, indicate if this is already listed in the Study Procedures Section, or describe the equipment.

N/A

6. Investigational Devices

Please list in the space below all Investigational Devices to be used on Subjects.

Investigational Devices

Protocol Title: Does Dapagliflozin Provide Additional Health Benefits To Dietary Counseling For Weight Loss?
Clinical Research Protocol Title: Dapagliflozin Promotes Favorable Health Benefits That Are Independent Of Weight Loss In Overweight/Obese Adults

Protocol Type: Biomedical

Date Submitted: 03/01/2018

Approval Period: Draft

Important Note: This Print View may not reflect all comments and contingencies for approval. Please check the comments section of the online protocol.
Questions that appear to not have been answered may not have been required for this submission.
Please see the system application for more details.

***** Drugs, Reagents, or Chemicals *******7. Drugs, Reagents, or Chemicals**

- a) Please list in the space below all investigational drugs, reagents or chemicals to be administered to subjects during this study.
- b) Please list in the space below all commercial drugs, reagents or chemicals to be administered to subjects during this study.

Drug Name	Dapagliflozin
Source (e.g., Pharmacy, Sponsor, etc.,)	AstraZeneca Pharmaceuticals LP
If not premixed, where will the material be mixed and by whom	Pre-mixed by Bristol-Myers Squibb Company
Manufacturer	Bristol-Myers Squibb Company
IND # (if available)	n/a
Dosage	5 mg/day of Dapagliflozin for the first 14-days, and then a dose increase to 10 mg/day of Dapagliflozin for remaining 10 weeks.
Administration Route	Oral
Y	Are these new or different uses of these commercially available drugs, reagents, or chemicals?
N	IND Regulations

Please read the IND Statements

***** Subject Population (a-g) *****

Protocol Title: Does Dapagliflozin Provide Additional Health Benefits To Dietary Counseling For Weight Loss?
Clinical Research Protocol Title: Dapagliflozin Promotes Favorable Health Benefits That Are Independent Of Weight Loss In Overweight/Obese Adults

Protocol Type: Biomedical

Date Submitted: 03/01/2018

Approval Period: Draft

Important Note: This Print View may not reflect all comments and contingencies for approval. Please check the comments section of the online protocol.
Questions that appear to not have been answered may not have been required for this submission.
Please see the system application for more details.

8.

Subject Population - In the space below, please detail the participants that you are requesting to recruit (include requested participant number and description of each group requested). (Input N/A if not applicable)

a) Requested Participant Description (Include number of participants that you plan to study and description of each group requested, if applicable).

60 overweight/obese adult volunteers (men and women) will be studied. However, the number enrolled may be higher in the event of enrollment of replacement subjects for dropout(s) that discontinued for reasons other than an adverse event due to study medication. In the event of a replacement subject being enrolled, this subject will complete all visits. Therefore we would like to enroll 200 participants.

Participants previously enrolled in 14-5531H and withdrawn due to new information will be contacted per for future enrollment in this study. Several procedures, such as screening and DEXA, OGTT, will not be redone, but will be released for the purposes of this purpose. You can find the participant letter that went out to those participants in the attachments section.

b) What is the rationale for studying the requested group(s) of participants?

Adults who are overweight/obese are at the greatest risk of developing type 2 diabetes, thus overweight/obese adults potentially have the most to gain should the outcome of the study prove favorable. Inclusion of adults already diagnosed with diabetes might complicate the interpretation of the data; that is, as a consequence of the patho-physiology associated with diabetes, the response to our feeding treatment with or without Dapagliflozin may differ in adults with diabetes compared with adults who are diabetes free.

c) If applicable, state the rationale for involvement of potentially vulnerable subjects to be entered into the study, including minors, pregnant women, economically and educationally disadvantaged, or decisionally impaired subjects. Specify the measures being taken to minimize the risks and the chance of harm to the potentially vulnerable subjects.

Potentially vulnerable subjects will not be studied.

d) If women, minorities, or minors are not included, a clear compelling rationale must be provided. Examples for not including minors: disease does not occur in children; drug or device would interfere with normal growth and development; etc.

Women and minorities will be invited to participate. Minors will be excluded. The prevalence of type 2 diabetes is greater in adults than minors. Safety and effectiveness of Dapagliflozin in pediatric patients under 18 years of age have not been established.

e) State if any of the subjects are students, employees, or laboratory personnel. They should be presented with the same written informed consent. If compensation is allowed, they should also receive it.

If any of the subjects are students, employees, or laboratory personnel they will be presented with the

Protocol Title: Does Dapagliflozin Provide Additional Health Benefits To Dietary Counseling For Weight Loss?
Clinical Research Protocol Title: Dapagliflozin Promotes Favorable Health Benefits That Are Independent Of Weight Loss In Overweight/Obese Adults

Protocol Type: Biomedical

Date Submitted: 03/01/2018

Approval Period: Draft

Important Note: This Print View may not reflect all comments and contingencies for approval. Please check the comments section of the online protocol.
Questions that appear to not have been answered may not have been required for this submission.
Please see the system application for more details.

same written informed consent; compensation is allowed, they will also receive it.

f) Describe how potential subjects will be identified for recruitment (e.g., chart review, referral from individual's treating physician, those individuals answering an ad). How will potential participants learn about the research and how will they be recruited (e.g., flyer, email, web posting, telephone, etc.)? Attach recruitment materials in the Attachment Section (#16). Important to remember: potential subjects may not be contacted before IRB approval.

Please see examples of recruitment materials in the attachment section.

Potential subjects will be recruited via electronic advertisement (e.g. The Source) and email lists (e.g. CSU genfac). If necessary, potential subjects may also be recruited via newspaper advertisement (e.g. The Coloradoan), clinical trials websites (e.g. clinicaltrials.gov), and/or flyers/posters placed in public places (e.g. coffee shops) in and around the Fort Collins area. Public places includes using approved recruitment texts in social media forums.

g) If applicable, provide rationale for the inclusion of healthy volunteers in this study. Specify any risks to which these healthy volunteers may possibly be exposed. Specify the measures being taken to minimize the risks and the chance of harm to these volunteers.

Adults who are overweight/obese but otherwise healthy will be invited to participate. Inclusion of adults already diagnosed with diabetes might complicate the interpretation of the data; that is, as a consequence of the patho-physiology associated with diabetes, the response to feeding with or without Dapagliflozin may differ in adults with diabetes compared with adults who are diabetes free.

It is not possible to identify all potential risks in research procedures, but the researcher(s) have taken reasonable safeguards to minimize any known and potential (but unknown) risks. The Human Performance Clinical Research Laboratory has emergency supplies including a medicine trolley equipped with heart machines and supplemental oxygen. The research team has a great deal of experience with all of the procedures. Some of the procedures for which you are being asked to volunteer have a number of associated risks:

Body Composition

The risks associated with the DEXA are very low. The maximum radiation dose you will receive in this study is less than 1/1000th of the federal and state occupational whole body dose limit allowed to radiation workers (5,000 mrem). Put another way, the maximum dose from any scan we utilize with this DEXA ranges from 1.2 mrem (Whole body scan) to 12.2 mrem (for several of the regional scans, such as lumbar, femur, and forearm scans). The average annual background radiation you already receive is at least 620 mrem/year. The more radiation you receive over the course of your life, the more the risk increases of developing a fatal cancer or inducing changes in genes. The radiation in this scan is not expected to significantly increase these risks, but the exact increase in such risks is not known. There are no discomforts associated with this procedure. Women who are or could be pregnant should receive no unnecessary radiation and should not participate in this study.

Women will complete a pregnancy test before participating in a DEXA scan.

Exercise Tests

Protocol Title: Does Dapagliflozin Provide Additional Health Benefits To Dietary Counseling For Weight Loss?
Clinical Research Protocol Title: Dapagliflozin Promotes Favorable Health Benefits That Are Independent Of Weight Loss In Overweight/Obese Adults

Protocol Type: Biomedical

Date Submitted: 03/01/2018

Approval Period: Draft

Important Note: This Print View may not reflect all comments and contingencies for approval. Please check the comments section of the online protocol.
Questions that appear to not have been answered may not have been required for this submission.
Please see the system application for more details.

There is a very small chance of an irregular heartbeat during exercise (< 1% of all subjects). Other rare risks of a stress test are heart attack (< 5 in 10,000) and death (<2 in 10,000). Wearing a mouthpiece and nose-clip can sometimes cause dryness in the mouth and mild discomfort. Difficult exercise may make you feel very tired, light headed and nauseous. Exhausting exercise will, by definition, make you feel very tired. After any exercise your muscles might ache.

ACSM guidelines pertinent to the requirement of physician supervised exercise (stress) testing will be followed.

Blood Collection

When the needle goes into a vein, it may hurt for a short period of time (a few seconds). Also there may be minor discomfort of having the needle/plastic tube taped to your arm. In about 1 in 10 cases, a small amount of bleeding will occur under the skin that will cause a bruise. The risk of forming a blood clot in the vein is about 1 in 100, and the risk of significant blood loss is 1 in 1,000. Additionally, there is a risk that you may faint while having blood collected or having the catheter inserted in your vein.

Only trained research personnel will be permitted to perform phlebotomy.

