be measured.

Visit 3: appetite and hunger will be assessed and participants will be given a 3-dietary record form to complete.

Visits 4-27: 12 weeks of nutrition counseling/weighing (upto 2 visits per week for 12 weeks). Concurrent with these visits, research participants will ingest, on a daily basis, either Dapagliflozin or placebo.

Visit 28: an oral glucose tolerance test will be performed and resting metabolic rate and blood pressure will be measured.

Visit 29: appetite and hunger will be assessed; body composition will be measured, and participants will be given a 3-day dietary record form to complete.

DETAILED DESCRIPTION OF STUDY PROCEDURES

Visit 1: study participants will provide informed consent and undergo screening: medical history, 12-lead electrocardiogram and blood pressure assessment at rest and during incremental exercise to volitional exhaustion, blood sampling, and measurement of body composition.

These screening procedures are standard for our lab. Each of the procedures is currently active in other IRB-approved protocols (e.g. 12-3767H, 08-611H, 14-4756H).

Health History - Potential participants will complete a standardized health history questionnaire that will address past and present medication use, allergies, past and present medical conditions and physical injuries, and habitual use of alcohol and tobacco.

Body composition - Percent body-fat, fat-free mass, total and regional adipose tissue mass, and total bone mineral density will be determined using a whole-body dual energy x-ray absorptiometry scan (DEXA, Model DPX-IQ Lunar Corp., Madison, WI).

Maximal graded exercise stress testing - A 12-lead ECG, arterial blood pressure (brachial sphygmomanometer) will be obtained during quiet resting conditions in the supine and upright sitting positions, and during incremental stationary cycle ergometer or treadmill exercise until volitional fatigue. During exercise, oxygen consumption, carbon dioxide production and ventilation may be determined by indirect calorimetry. All data from these tests will be reviewed by a cardiologist. Only those subjects demonstrating no signs or symptoms of disease will be invited to participate in the study.

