Blood sampling – Blood (~ 20 ml) will be sampled from an antecubital or hand vein for subsequent analysis of circulating factors pertinent to inclusion/exclusion criteria, including glucose, aspartate aminotransferase, alanine aminotransferase, and total bilirubin. These blood analyses will be performed in on-site (Piccolo Xpress, Abaxis, Union City, CA). Testing for Hepatitis B/C will be performed at a local, external clinical lab (e.g. University of Colorado-Health North). Per the Medical Monitor's discretion follow up blood draws maybe requested.

Visit 2: Resting Metabolic Rate (ventilated hood technique, indirect calorimetry) for 45 minutes and blood pressure will be measured. An oral glucose tolerance test will be performed.

Protocol Title:	Does Dapagliflozin Provide Additional Health Benefits To Dietary Counseling For Weight Loss? Clinical Research Protocol Title: Dapagliflozin Promotes Favorable Health Benefits That Are Independent Of Weight Loss In Overweight/Obese Adults
Protocol Type:	Biomedical
Date Submitted:	03/01/2018
Approval Period:	Draft
Important Note:	This Print View may not reflect all comments and contingencies for approval. Please check the comments section of the online protocol. Questions that appear to not have been answered may not have been required for this submission. Please see the system application for more details.

These procedures are standard for our lab. Each of the procedures is currently active in other IRB-approved protocols (e.g. 14-5201H).

Blood pressure will be determined three times using the left arm via standard procedures. Each assessment will be separated by 3 minutes. The mean of the three measurements will be recorded.

Participants will report to the laboratory early in the morning, following a 12-hour fast and 24-hour abstention from exercise. An intravenous catheter will be inserted into an antecubital or hand vein and kept patent with a saline drip. Following baseline blood sampling for fasting glucose and insulin, participants will ingest 75 g of dextrose dissolved in 250 ml of water over 10-minutes. Venous blood (~ 9 ml) will be sampled at time 0 (baseline) and 5, 10, 15, 20, 30, 45, 60, 75, 90 105 and 120 minutes for determination of concentration of blood glucose (2300 STAT Plus Glucose Lactate Analyzer, YSI Inc., Yellow Springs, Ohio), and insulin (commercially available assay).

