On a day different to the oral glucose tolerance day, participants will report to the laboratory early in the morning, following a 12-hour fast and 24-hour abstention from exercise. An intravenous catheter will be inserted into an antecubital or hand vein and kept patent with a saline drip. Participants will be provided with a standardized "priming meal" comprising a commercially available, mixed-nutrient liquid meal, dosed to 1 kcal per kg body mass (Ensure, Ross Laboratories, Abbott Park, IL; 64% CHO, 22% fat, 14% protein). One hour following consumption of this priming meal, participants will be presented with a pre-weighed buffet of food from which they will have opportunity to eat ad libitum quantities over a 30 minute period. The remaining uneaten food will be reweighed and participants' energy and macronutrient intakes will later be determined using the Food Intake Analysis System software (U Texas Health Sciences Center, Houston). Prior to the standardized primer meal, and to the buffet, and then every 60 minutes over 3 hours following the buffet, participants will be asked to rate their perceptions of hunger and satiety using a visual analog scale. At these same time points, venous blood (~ 20 ml) will be sampled, and plasma/serum isolated and stored at -70°C for subsequent determination of concentrations of hunger and satiety hormones (e.g. ghrelin, peptide YY, leptin, and insulin). At the conclusion of these tests, the study participant will give a form in which to record the amounts of food and beverage (except water) they eat and drink for three consecutive days, including 2 week days and 1 weekend day. Upon completion of the food records, the form will be returned to the research team. This information will be used to establish baseline dietary intake and will be useful information for the nutrition counselors seeking to help the participants lose weight.

Protocol Title: Does Dapagliflozin Provide Additional Health Benefits To Dietary Counseling For Weight Loss?
Clinical Research Protocol Title: Dapagliflozin Promotes Favorable Health Benefits That Are Independent Of Weight Loss In Overweight/Obese Adults

Protocol Type: Biomedical

Date Submitted: 03/01/2018

Approval Period: Draft

Important Note: This Print View may not reflect all comments and contingencies for approval. Please check the comments section of the online protocol.
Questions that appear to not have been answered may not have been required for this submission.

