Please see the system application for more details.

Visits 4-27: During the first 6 weeks participants will meet with a study counselor 2 times per week for dietary counseling and measurement of body weight. During the second 6-week period they will meet 1-2 times per week for dietary counseling and body weight measurement, depending on whether or not they are meeting weight loss goals. If they are losing weight as prescribed, they will meet only once per week, but if they are not meeting weight loss goals they will meet 2 times per week. Participants will need to fast for 10 hours prior to the weigh-in. On 2 random counseling occasions between weeks 4 and 10, they will be asked to recall what they ate during the previous 24 hours. If participants fail to achieve their target body weight (within 1 kg or 2.2 lbs) on three consecutive weighing sessions, they will be provided with additional counseling and instructions to aid in achieving your target body weight.

During the first two weeks of the 12 week intervention, participants will ingest one pill daily (5 mg DAPA) and for the remaining 10 weeks participants will ingest 2 pills daily (a total of 10 mg DAPA). On 3 random weigh-in occasions between weeks 4 and 10, participants will be asked to recall what they ate during the previous 24 hours.

Visit 28: Resting Metabolic Rate Test, Oral Glucose Tolerance Test, and Blood Pressure will be measured (e.g. the final week of daily ingestion of Dapagliflozin). See description of Visit 2.

Visit 29: in the HPCRL appetite and hunger will be assessed this visit will occur in week 12 (e.g. during the final week of daily ingestion of Dapagliflozin). Body composition will be measured at this visit or early the following week (e.g. week 13). The study participants will also be given the 3-day food intake record form to be completed and returned to the research team.

b) Explain why human subjects must be used for this project.

Dapagliflozin is approved for human use. Due to potential species differences it would not be appropriate to perform these studies on experimental animals.

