*** Subject Population (h-m) ***

8. Subject Population (Input N/A if not applicable)

h) Inclusion and Exclusion Criteria (e.g., Participants must have 20/20 vision, Participants must be 30-45 years of age, etc.)

Identify inclusion criteria.

For inclusion in the study subjects should fulfill the following criteria:

1. Provision of informed consent prior to any study specific procedures.
2. Aged 18-65 years.
3. No known Type 2 Diabetes
4. Body mass index greater than or equal to 27.5 kg/m²
5. Limited exercise participation (maximum of 3/week regularly scheduled activity sessions of < 30 minutes during the previous month).
6. Completion of a screening visit consisting of medical history, physical examination, and 12-lead electrocardiogram and blood pressure assessment at rest and during incremental exercise to volitional exhaustion (Note: Subjects with abnormal screening values may be eligible if the results are not clinically significant, as judged by the investigator or medical monitor)
7. Agree to abide by the study schedule and dietary restrictions and to return for the required assessments
8. Women of childbearing potential must have negative pregnancy test and be using acceptable contraception

Protocol Title: Does Dapagliflozin Provide Additional Health Benefits To Dietary Counseling For Weight Loss?
Clinical Research Protocol Title: Dapagliflozin Promotes Favorable Health Benefits That Are Independent Of Weight Loss In Overweight/Obese Adults

Protocol Type: Biomedical

Date Submitted: 03/01/2018

Approval Period: Draft

Important Note: This Print View may not reflect all comments and contingencies for approval. Please check the comments section of the online protocol.
Questions that appear to not have been answered may not have been required for this submission.
Please see the system application for more details.

Identify exclusion criteria.

Subjects should not enter the study if any of the following exclusion criteria are fulfilled:

1. Evidence of clinically significant cardiovascular, respiratory, renal, hepatic, pulmonary, gastrointestinal, haematological, neurological, psychiatric, or other disease that may interfere with the objectives of the study or the safety of the subject, as judged by the investigator in agreement with the sponsor or medical monitor, have been hospitalized in the past 2 years as a result of these conditions, or are receiving pharmacological treatment for these conditions.

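### Returning 14-5531H participants are excused repeat screening with no age limit on the old results, and no scheduled pre-dose step re-checks history, medication, liver tests or pregnancy

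*Combined protocol and SAP*

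**What the plan says.** Section 8(a) (Subject Population) plans to contact participants withdrawn from 14-5531H and enrol them here. For them, "Several procedures, such as screening and DEXA, OGTT, will not be redone"; the earlier results are released to this study. No limit is put on how old those results may be. The same section says of replacement subjects: "In the event of a replacement subject being enrolled, this subject will complete all visits".

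The entry checks that the waiver touches are described in these places:

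- **History and medication** (section 2(a), Visit 1): "Potential participants will complete a standardized health history questionnaire that will address past and present medication use, allergies, past and present medical conditions".
- **Liver tests** (section 2(a), Visit 1): blood is drawn for "circulating factors pertinent to inclusion/exclusion criteria, including glucose, aspartate aminotransferase, alanine aminotransferase, and total bilirubin". The medical monitor may ask for follow-up draws.
- **Pregnancy test tied to a procedure** (section 8(g)): "Women will complete a pregnancy test before participating in a DEXA scan".
- **Pregnancy test as an entry criterion** (section 8(h), inclusion 8): "Women of childbearing potential must have negative pregnancy test and be using acceptable contraception". No visit is named.

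Section 8(h) also has criteria that depend on current information. Exclusion 2 looks back 2 weeks for prescription drugs and herbal preparations, and 4 weeks for weight-loss products, both from study commencement. Exclusion 3 looks back 30 days from the screening visit for other investigational drugs. Exclusions 9 and 10 set limits for AST, ALT and bilirubin. Exclusion 16 sets a blood pressure limit at randomisation.

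**The concern.** The waiver is an explicit rule, not a silence. It removes the one visit at which most of the safety-related entry criteria are checked, and nothing states how old the substituted results may be. Someone could have begun a new medicine, developed a liver problem or become pregnant since the 14-5531H screening, and the described procedures would not bring this to light before the first dose.

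Entry checks carry weight in this trial. Participants are overweight or obese but otherwise healthy, and the investigator rates the risk as above minimal. There is no data safety monitoring board, and the special-precautions item is answered as not applicable.

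**Working it through.** The plan gives no figure on this point, so the check is mainly of text: list every described procedure before dosing, remove what section 8(a) waives, and see what is left for each criterion. Dosing runs alongside Visits 4-27, so the pre-dose visits are 1, 2 and 3.

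**What remains at each pre-dose visit for a returner**

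- Visit 1 is the screening visit: history, ECG and blood pressure at rest and during exercise, screening blood, and DEXA. Screening and DEXA are both named in the waiver.
- Visit 2 is resting metabolic rate, blood pressure and the OGTT. The OGTT is waived. The other Visit 2 blood is for inflammation and oxidative-stress markers, not liver tests.
- Visit 3 is the appetite assessment. Its blood is taken "for subsequent determination of concentrations of hunger and satiety hormones (e.g. ghrelin, peptide YY, leptin, and insulin"). It includes no history questionnaire, liver test or pregnancy test.

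**Result by criterion**

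- *Medical history and medication (exclusions 1 and 2).* The criteria apply. The only described questionnaire is at Visit 1, so no scheduled step remains.
- *AST, ALT and bilirubin (exclusions 9 and 10).* The criteria apply. The only scheduled tests are at Visit 1. Follow-up draws are discretionary.
- *Pregnancy (inclusion 8).* The criterion applies. Its only procedure-level trigger before dosing is the baseline DEXA, which is waived. The next DEXA is at Visit 29 or just after: "Body composition will be measured at this visit or early the following week (e.g. week 13"). That is after the drug has been taken for about 12 weeks.
- *Other investigational drugs (exclusion 3).* The first half, current enrolment elsewhere, is covered by the question in section 8(j). The 30-day half counts from the screening visit, and the text does not say which visit that is for someone not screened in this study.
- *Blood pressure (exclusion 16).* Re-checked at randomisation. This is the one criterion with its own dated limit at that point.

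**An illustration of age.** The 14-5531H screening dates are not given. Assume that they are no later than the date on which this protocol was cloned from 14-5531H, 27 February 2017 (Event History). First approval was on 25 April 2017.

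- 27 February to 27 March = 28 days; 27 March to 25 April = 29 days; 28 + 29 = 57 days.
- Exclusion 2 look-backs: 2 × 7 = 14 days and 4 × 7 = 28 days.
- 57 > 28 > 14.

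On that assumption, no 14-5531H questionnaire could answer either look-back in exclusion 2, even for the first person enrolled. Earlier screening or later enrolment would only lengthen the gap.

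**The case against.** The strongest reply is that the criteria were never waived. Inclusion 8 demands a negative pregnancy test whether or not a DEXA is done, and it makes no exception for returners. Exclusion 2 counts back from study commencement, so on a natural reading staff must ask again. Both points stand. A reader might infer from the waiver that returners are exempt from the criteria, or that a woman may enrol with no pregnancy test. The documents do not say that. What is missing is a named visit or procedure at which compliance is shown. For the liver criteria even the natural-reading argument is weaker, because exclusions 9 and 10 carry no time anchor that would force a new test.

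Second, other safeguards remain: blood pressure limits at randomisation, discretionary follow-up bloods, the general power to exclude under exclusion 5, and the medical monitor's judgement of dehydration risk under exclusion 17. These are real, but none is a scheduled history, liver test or pregnancy test, and judgement is only as good as the information it is given.

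Third, it is tempting to read the waiver as covering every returner. Section 8(a) has replacement subjects complete all visits, so a returner who enters as a replacement would on its face attend Visit 1. The text does not say which sentence prevails in that case. The point is therefore confined to returners who are not replacements.

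Fourth, section 8(i) defers to an attached screening document. The attachment list includes a study-specific medical screening form dated 25 April 2017, the sponsor's protocol and the participant letter, and there is a consent form. None was available for this review, and any of them may contain a re-check. This limits confidence in a claim of absence.

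**Conclusion.** The point holds in a limited form. Section 8(a) excuses returning 14-5531H participants from repeat screening, DEXA and OGTT and sets no maximum age for the reused results. The eligibility criteria still apply to them. For a returner who is not a replacement subject, however, the protocol as supplied schedules no pre-dose step that repeats the history and medication review or the AST, ALT and bilirubin tests. It also names no visit for the pregnancy test that inclusion 8 requires.

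The size cannot be measured: neither the number of returners nor any 14-5531H screening date is given. The 57-day figure rests on the clone-date assumption. It shows only that old records cannot answer exclusion 2; it does not measure risk. A reader might go further and infer that people were dosed on results one or two years old. The documents give no enrolment date for any returner and do not support that.

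This should be amended, because the rule is explicit, the checks concern safety and the remedy is cheap. Confidence is medium, because the unseen attachments may already close the gap.

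**What to change.** Amend section 8(a) so that, before randomisation and first dose in this study, each returner:

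1. repeats the history and medication questionnaire, including use of weight-loss products and recent cardiovascular events;
2. gives the Visit 1 screening blood sample again; and
3. if a woman of childbearing potential, has a pregnancy test.

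State that the 30-day window in exclusion 3 counts back from entry to this study. Say also whether a returner who enters as a replacement follows the waiver or completes all visits. The exercise stress test and DEXA need not be repeated for this purpose. If the screening form, sponsor protocol, participant letter or consent form already requires these checks, a cross-reference in section 8(a) is enough.

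The cost is a one-paragraph amendment and at most one short visit for an unknown number of returners, using procedures the trial already runs. A few returners may prove ineligible.
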